### ***8.3.2.3 Assessment of Severity (Intensity)***

The severity of an adverse event is defined as a qualitative assessment of the level of discomfort of an adverse event as is determined by the Investigator or reported to him/her by the subject. The assessment of intensity is made irrespective of study medication relationship or seriousness of the event. The investigator will make an assessment of intensity for each AE and SAE reported during the study and assign it to 1 of the following categories: and should be evaluated according to the scale in Table 3.

**Table 3: Assessment of Severity (Intensity)**

Mild	An event that is easily tolerated by the participant, causing minimal discomfort and not interfering with everyday activities.
Moderate	An event that causes sufficiently discomfort and interferes with normal everyday activities.
Severe	An event that prevents normal everyday activities. An AE that is assessed as severe should not be confused with a SAE. Severe is a category utilized for rating the intensity of an event; and both AEs and SAEs can be assessed as severe.

Please note: the term “severe” is used to describe the intensity (severity, see above) of an event/reaction; the event/reaction itself may be of relatively minor medical significance (such as severe headache). This is not the same as a “Serious” Adverse Event, which is based on subject/event outcome or action criteria usually associated with events that pose a threat to the subject’s life or vital functions. “Serious” (NOT severity) serves as a guide for defining regulatory reporting obligations. An event is defined as ‘serious’ when it meets at least 1 of the predefined outcomes as described in the definition of an SAE, NOT when it is rated as severe.

### 8.3.3 Expedited reporting of Serious and Unexpected Adverse Events

#### Safety reports

An investigator must immediately report to the Sponsor or Sponsor representative any serious adverse event, whether or not considered drug-related, including those listed in the protocol or investigator brochure and must include an assessment of whether there is a reasonable possibility that the drug caused the event. Study endpoints that are serious adverse events (e.g., all-cause mortality) must be reported in accordance with the protocol unless there is evidence suggesting a causal relationship between the drug and the event (e.g., death from anaphylaxis). In that case, the Investigator must immediately report the event to the Sponsor. The investigator must record non-serious adverse events and report them to the Sponsor according to the timetable for reporting specified in the protocol. In case of incomplete information, the Investigator must provide follow-up information as soon as possible, again using the SAE report form.

This requirement applies to occurrences observed during the course of the study and within four (4) weeks of last administration of the study medication.

In addition, in the case of immediately life-threatening AEs or AEs with fatal outcome, or adverse events that are serious, unexpected (i.e., not in the Clinical Investigator’s Brochure) and judged related to the investigational product, the Investigator must inform the Sponsor or Sponsor representative by phone within 24 hours of observation or occurrence of the SAE.

SAEs must be reported to the IRB/EC according to the IRB/EC requirements.

The Investigator/designee will forward all source documents (redacted, if necessary, to maintain the blind) related to the SAE to the Medical Monitor. For each SAE and follow-up to an SAE, the site should ensure that an SAE Narrative and critical baseline CRFs are completed as of the onset date for the SAE (e.g., demographics, concomitant medications, and medical history) and emailed

to [name] (see address below). All SAEs must be reported to [name] via phone or e-mail within 24 hours of becoming aware of the event, whether or not the serious events are deemed drug related. Send to:

[name], FACS

#### 8.3.4 Follow-up of subjects after adverse events

If an adverse event/adverse reaction occurs, the Investigator will institute support and/or treatment as deemed appropriate. If a non-serious adverse event/adverse reaction is unresolved at the time of the last visit, efforts will be made to follow up until the adverse event/adverse reaction is resolved or stabilized, the subject is lost to follow-up, or there is other resolution to the event.

## 9 Statistics

### 9.1 Primary Hypotheses

H01: The percentage of subjects with positive outcomes is NOT different between subjects treated with AG-920 and Proparacaine.

H11: The percentage of subjects with positive outcomes is different between subjects treated with AG-920 and Proparacaine.

The primary hypotheses outlined above are based on a controlled trial design for superiority of testing. The current study has an active-control treatment with the intention to compare the treatment of AG-920 in reference to the active-control treatment of Proparacaine, rather than testing for superiority against the latter.

The experimental hypothesis of this study focuses thus on the primary null hypothesis (H01) outlined above and intends, for simplicity, to accept the null hypothesis (H01) without a pre-defined non-inferiority margin should the null hypothesis (H01) is NOT rejected at a statistically significant level of 0.05 (2-sided).

### 9.2 Sample Size Considerations

The sample size of approximately 70 subjects to be randomized in a 1:1 allocation ratio for AG-920 and reference groups is as directed by the U.S. FDA for a Pediatric Study Plan, rather than being estimated based on a pre-defined non-inferiority margin commonly used for the trial design of therapeutical equivalence. The Sponsor plans to enroll up to 70 subjects in order to obtain at least 60 evaluable subjects.

### 9.3 *Analysis populations*

Randomized Population: The randomized population will include all subjects who were randomized to treatment. Baseline (screening) variables and demographic characteristics will be summarized for this population.

Intent-to-Treat Population (ITT): The ITT population will include all randomized subjects who have received at least one dose (two drops) of study medication. This population will be the primary population for the efficacy analyses and all efficacy variables will be summarized using this set of subjects. The ITT population will include subjects as randomized.

Per-protocol population (PP): The PP population is a subset of the ITT population, which will include those subjects (and their visits) who do not have major protocol violations likely to seriously affect the primary outcome of the study as judged by a masked evaluation prior to the unmasking of the study treatment. This population will be the secondary population for efficacy analyses and all efficacy variables will be summarized using this set of subjects. If the PP and ITT populations are exactly the same and there are no missing data, then additional efficacy analyses on the PP population will not be performed. The PP population will include subjects as treated.

Safety Population: The safety population will include all randomized subjects who have received at least one drop of study medication. This population will be used to summarize the safety variables and will summarize subjects as treated.

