### 2.9.1 Primary efficacy analysis

The primary efficacy endpoint for this study is the proportion of subjects with anesthetic effect that is adequate for eye exam as assessed by the PI at 2-4 minutes post application of the dose. The definition of the primary efficacy endpoint is given in [Section 2.6.1](#). The non-parametric Cochran-Mantel-Haenszel (CMH) test with adjustment for study eye side will be used to examine the difference and/or therapeutic equivalence in proportion of subjects with anesthetic effect at 2-4 minutes post dose between the active treatment group and active-control group.

In primary efficacy analysis, rather than to reject the null hypothesis when there is a difference ( $P \leq 0.05$ ) between AG-920 and active-control treatments, this study is designed to accept the null hypothesis that there is no difference in anesthetic effect between AG-920 and active-control treatments ( $P > 0.05$ ), indicating the therapeutic equivalence of AG-920 to Proparacaine without reference to a pre-defined non-inferiority margin.

To further measure the therapeutical equivalence of anesthetic effect of AG-920 to the active-control treatment, between-group difference and its 95% confidence interval (CI) as well as its 90% CI in the proportion of subjects with anesthetic effect (yes=1) vs. non-effect (no=0) will be calculated using a two-way analysis of variance (ANOVA) model with treatment (the effect of interest) and study eye side as the effects. The study-eye-side effect is used as a blocking factor in the model to control the potential treatment differences among the study eye sides. The conventional 90% CI of the between-group difference will be used to measure the extent of the equivalent margin or non-inferiority margin of anesthetic effect of AG-920 to Proparacaine. The conventional rule of the 90% CI of the between-group difference lying

within +/-20% of the reference treatment will be employed to claim the therapeutic equivalence or non-inferiority of AG-920 to Proparacaine.

The primary efficacy analysis will be performed for the ITT population, which will include all randomized subjects who received the complete application of one study dose (i.e., two drops). The analysis model adjusts for the effect of the study eye side. The study-eye-side by treatment interaction will be examined through the summary descriptive statistics of subjects with anesthetic effect for each study eye side.

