### **2.9.3 Safety analysis**

#### Treatment Exposure

Frequencies of exposure to the study medication will be calculated based on the number of drops the subject has received over the course of the study. Frequencies of exposure will be categorized as the following: 1 drop and 2 drops. Frequencies of exposure will be summarized by treatment for the safety population defined in [Section 3.1](#), as well as for each gender group.

Compliance rates will be calculated by dividing the number of drops received by the number of drops that should have been given during the application of dose. Compliance rates will be summarized.

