##### Intention-to-treat (ITT) Population

This population is defined as all subjects who are randomized to treatment and have received at least one dose (2 drops) of the study medication. The ITT population is the primary population for efficacy evaluation in this study. Treatment identification is defined in the ITT population by treatment assignment. The ITT population will be identified and finalized before the database is locked and the treatment assignment is merged into the study database.

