#### 3.2 Screening and Enrollment

A screening summary including the number of subjects screened for study participation will be presented by site ([Table 1.1.1](#)).

An enrollment summary including the number of subjects enrolled/randomized, treated, and completing the study will be presented for all enrolled subjects and by site ([Table 1.1.2](#)). Enrolled subjects include those individuals who are screened and randomized into the study. The number of subjects treated with at least one drop of the dose of the study medication (i.e., the safety population) will be summarized for each treatment group and overall ([Table 1.1.3](#)). The number of subjects treated with at least one dose (2 drops) of the study medication (i.e., the ITT population) will be summarized for each treatment group and overall ([Table 1.1.4](#)). The number of subjects in the PP population will be summarized for each treatment group and overall ([Table 1.1.5](#)).

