### **3.7 Protocol Deviations and Violations**

A summary of protocol deviation and violations will be provided for the ITT population (Table 1.5.1). Subjects who are randomized to receive single-masked treatment in the study and included in the ITT population but do not have two drops of IMP dosed and/or post-dose status of anesthetic effect assessment will be listed for subjects randomized (Listing 4).

Subjects who are included in the ITT population but not included in the PP population due to either protocol violations or other reasons will be listed for all subjects excluded from the PP population (Listing 5).

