## 4.2 Treatment Compliance

The compliance rate during treatment will be summarized by treatment group and demographic parameters for the safety and ITT populations ([Tables 1.5.2](#) and [1.5.3](#)).

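### The primary ITT set requires both drops, so a child who stops after the first drop is in no efficacy analysis; the missing-outcome wording also conflicts (LOCF against scored as NO)

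*Protocol*

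**What the plan says.** **Who is in the primary set.** Protocol 9.3: "The ITT population will include all randomized subjects who have received at least one dose (two drops) of study medication". The ITT definition in SAP 3.1 covers subjects "randomized to treatment and have received at least one dose (2 drops) of the study medication", and SAP 2.9.1 and 3.2 repeat the two-drop condition. The per-protocol (PP) set is nested in ITT in both documents, and the efficacy subgroups are ITT subgroups. One drop is enough for the Safety set, which serves safety variables only.

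**One-drop exposure is foreseen.** The exposure paragraph of SAP 2.9.3 states: "Frequencies of exposure will be categorized as the following: 1 drop and 2 drops".

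**Two planned outputs sit badly with the definition.** SAP 3.7 plans a listing of randomised subjects "included in the ITT population but do not have two drops of IMP dosed and/or post-dose status of anesthetic effect assessment". SAP 4.2 states: "The compliance rate during treatment will be summarized by treatment group and demographic parameters for the safety and ITT populations".

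**Missing outcomes.** Protocol 9.5 imputes missing Day 1 data in ITT by last observation carried forward, and the titles of Tables 2.1.1 and 2.1.3 carry the LOCF label. SAP 2.8 scores a value missing through invalid data or early termination as NO, and SAP 2.9.1 points to 2.8. The last sentence of 2.8 then says that resultant missing data, efficacy included, are treated as missing. PP uses observed data only.

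**The concern.** Whether a child counts is decided by whether the second drop was given, and that can depend on how the first drop was tolerated. Protocol 1.2 lists stinging or burning for both products, and only the child and guardian are masked (Protocol 3.5). Stopping could therefore differ by arm, in a direction that cannot be known in advance.

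The trial claims equivalence. If more children stop on AG-920, leaving them out moves the observed difference toward zero and favours the claim. If more stop on Proparacaine, it hides a difference in favour of AG-920. No planned efficacy analysis would show either.

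The missing-outcome wording is a smaller matter, but it leaves the primary table labelled with a method that cannot be carried out on this endpoint.

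**Working it through.** **Step 1: follow a child who receives one drop.** Safety: in. ITT: out, because both drops are required. PP: out, because it is a subset of ITT. Subgroups: out, because they are ITT subgroups. The NO rule of SAP 2.8 operates within the set analysed, so it never applies to this child.

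**Step 2: compare the ITT definition with SAP 3.7 and 4.2.** The first limb of SAP 3.7 (in ITT, two drops not dosed) describes nobody under SAP 3.1, which is a contradiction. The second limb (no post-dose assessment) is consistent with a two-drop ITT. Table 1.5.3, drop compliance in ITT, is 2/2 = 100% for everyone. It is uninformative rather than contradictory.

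**Step 3: a two-drop child with no assessment.** Under Protocol 9.5 there is no earlier value of the endpoint to carry forward. Under the NO rule of SAP 2.8, 34 YES plus this child gives 34/35 = 97.1%. If the last sentence of 2.8 overrode that rule, the result would be 34/34 = 100%.

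**Step 4: possible size.** The plan has no response rate, power or stopping rate to reproduce, so every rate here is assumed.

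Inputs from the documents: up to 70 randomised 1:1 (35 per arm), about 30 per arm evaluable; Pearson chi-square at two-sided 0.05 (Protocol 9.4.6); 90% CI from an ANOVA with treatment and eye side, to lie within ±20% of the reference (SAP 2.9.1). The limit is read as 0.20 × the Proparacaine rate.

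Assumptions: k children stop on AG-920 only and none has a recorded answer. The number of other NO answers is the same in each arm. Eye side is balanced and has no effect.

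Formulas: d = pA − pP; s² = [nA·pA(1−pA) + nP·pP(1−pP)]/(N−3); 90% CI = d ± t(0.95, N−3)·s·√(1/nA + 1/nP).

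Worked case, 35 per arm, one other NO per arm, k = 4, stops counted as NO: 30/35 against 34/35.
- d = 0.857 − 0.971 = −0.114
- s² = (4.286 + 0.971)/67 = 0.0785
- SE = √(0.0785 × 2/35) = 0.0670; t = 1.668
- CI −22.6 to −0.3 points; limit 0.20 × 97.1 = 19.4; fails. Chi-square p = 0.088.
- As written (stops excluded): 30/31 against 34/35, d = −0.4 (−7.6 to 6.9); passes.

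Smallest k at which the ±20% rule fails:

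| Per arm | Other NO per arm | k | Stops counted as NO: d (90% CI) | Limit | p | As written: d (90% CI) |
|---|---|---|---|---|---|---|
| 35 | 0 | 4 | −11.4 (−20.6 to −2.3) | 20.0 | 0.039 | 0, no failures |
| 35 | 1 | 4 | −11.4 (−22.6 to −0.3) | 19.4 | 0.088 | −0.4 (−7.6 to 6.9) |
| 35 | 2 | 3 | −8.6 (−20.7 to 3.5) | 18.9 | 0.232 | −0.5 (−10.4 to 9.4) |
| 30 | 0 | 4 | −13.3 (−24.0 to −2.7) | 20.0 | 0.038 | 0, no failures |
| 30 | 1 | 3 | −10.0 (−22.0 to 2.0) | 19.3 | 0.161 | −0.4 (−8.8 to 8.0) |
| 30 | 2 | 2 | −6.7 (−19.9 to 6.5) | 18.7 | 0.389 | −0.5 (−11.9 to 11.0) |

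If the limit is read as 20 percentage points, the last row passes and the others are unchanged.

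Cases that do not change the conclusion at 35 per arm: with no other NO, k = 1, 2, 3 give lower limits of −7.7, −12.4 and −16.6 and p = 0.314, 0.151 and 0.077. With one other NO per arm, k = 3 gives −18.9 against 19.4. With two, k = 2 gives −17.1 against 18.9. Stops of 4 against 1 with no other NO give 31/35 against 34/35: −8.6 (−18.9 to 1.8), p = 0.164, limit 19.4.

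**Step 5: how firm is the first row?** With the four NOs split 2/2 by eye, the Cochran-Mantel-Haenszel (CMH) p is 0.042. With eye sides split 20/15 on AG-920 and 15/20 on Proparacaine, and all four NOs in the 20-child AG-920 stratum, CMH p is 0.070 and the 90% CI is −19.0 to −1.0, so both rules pass. Fisher's exact p is 0.114. As written there is no failure in either arm, so chi-square and CMH are undefined and the P > 0.05 rule cannot be evaluated.

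**The case against.** The strongest reply is that this hardly matters in practice. Dosing takes 30 seconds and is done by staff, Protocol 9.5 expects minimal missing data, and no document suggests that 4 of 35 children (11%) would stop in one arm and none in the other. That stands, and it is why the figures are illustrative.

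Nor would the children vanish. Tables 1.1.3, 1.1.4 and 3.1.1 allow a count by arm. The early-termination listing shows treatment and drops received, Listing 3 covers all subjects randomised, and the tabulation of the PI's assessment (Data 8.1) has no stated ITT restriction. What is missing is a planned analysis, not the data.

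Four stronger readings are tempting and the documents do not support them:
- A reader might infer that SAP 3.7 and Table 1.5.3 both presuppose one-drop children in ITT. Only the first limb of 3.7 does.
- A reader might count three competing missing-data rules. The last sentence of SAP 2.8 can be read as covering only what remains after the NO rule. It needs clarifying, but the firm conflict is LOCF against NO. Because Protocol 9.4.1 leaves fuller description of methods to the SAP, that conflict is mainly clean-up.
- A reader might see a contradiction in timing the exam from the last drop (Protocol Table 1, 6.4.3.1) or from the second drop (SAP 2.2, 2.3). For a fully dosed child these are the same drop; they part only for a child who stops early.
- A reader might conclude that four one-sided stops at 35 per arm defeat both equivalence rules. With no other NO, that depends on the eye split.

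It is also fair that a one-drop threshold still conditions on something after randomisation. It does, but a child who received nothing cannot have stopped because of how the product felt, and the remaining exclusions can be reported by arm.

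**Conclusion.** The point holds and should be fixed. The set called ITT is a completed-dose set: it omits a type of child the SAP itself foresees and places that child beyond its own NO rule. The first limb of SAP 3.7 contradicts the definition. LOCF cannot be applied to an endpoint assessed once.

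On size, 3 to 4 one-sided stops at 35 per arm, or 2 to 4 at 30 per arm, are enough to fail the ±20% rule. This rests on stops in AG-920 only, no recorded answer for any of them, 0 to 2 other NO per arm, and the limit read as a fraction of the Proparacaine rate. The documents do not show that such stopping is likely or that it would favour AG-920, so this is a preventable weakness in the equivalence claim and not a demonstrated bias.

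**What to change.** 1. Define the primary efficacy set as all randomised subjects who received at least one drop, analysed as randomised. Report never-dosed subjects by arm; Table 1.1.2 is planned only overall and by site.
2. Use the PI's recorded YES or NO whenever there is one, including for a one-drop child. Count as NO only a subject with no valid assessment. This is the existing SAP 2.8 rule applied to the wider set.
3. Delete LOCF from Protocol 9.5 and from the titles of Tables 2.1.1 and 2.1.3, and refer to SAP 2.8. Limit the last sentence of 2.8 to safety parameters.
4. Conform SAP 2.9.1, 3.1, 3.2 and the title of Table 1.1.4. SAP 3.7 and Table 1.5.3 then work as written. As minor wording, make the last-drop and second-drop descriptions of exam timing agree between the documents.
5. Keep PP as a supportive analysis on observed data, and carry the SAP's completed-treatment condition into Protocol 9.3. State that PP also drops major violators and is analysed as treated, so it does not isolate the effect of one-drop children.

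Cost: wording changes and one by-arm count. No new data are needed, since drops received and the PI's answer are already collected. The observed success rate may be slightly lower, and the ITT and Safety tables will largely duplicate each other.

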### 9.4.6 Analysis of Efficacy

Analyses will be performed primarily on the ITT population and will be repeated on the PP population to determine robustness of results. For the primary efficacy endpoint of the proportion of subjects in whom there was adequate local anesthetic effect to perform an eye exam for which the subject is seeing the ophthalmologist, a Pearson chi-square test will be used for the comparison of the two proportions from the two treatment groups. In addition, a two-sided 95% confidence interval for the difference in response rates between the two treatment groups will be calculated. If the difference in response rates is around zero and the *P* value is NOT statistically significant (i.e.,  $P > 0.05$ ), then the therapeutical equivalence of AG-920 to the Proparacaine will be claimed, without reference to a pre-defined non-inferiority margin. The 95% CI of the difference in response rates will be reported to measure the extend or margin of the efficacy equivalence of AG920 to Proparacaine.

Sub-group analyses based upon pre-study characteristics such as sex, iris color, age, and race may be completed to further investigate the efficacy and safety measures.

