Prior to the determination of the primary efficacy variable, handling of missing values that occur prior to eye exam is described in [Section 2.8](#).

The primary efficacy endpoint will also be analyzed for the PP population as well as for subgroups of the ITT population, such as male vs. female, Caucasian vs. Non-Caucasian, age groups, and iris color dark brown vs. other colors.

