##### Per-Protocol (PP) Population

This population is defined as a sub-population of the ITT population. The PP population is the secondary population for efficacy evaluation in this study and will be defined as all randomized subjects who completed the study treatment with no major protocol violations likely to seriously affect the primary outcome of the study as judged by the investigator. In case there is a difference between treatment assigned and received, treatment actually received will be utilized to define the treatment identification in the PP population. In case there are missing data in efficacy measures, the analysis of the PP population will be based on observed or actual data only (without imputation). The PP population will be identified and finalized before the database is locked.

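### No rule makes the no-difference claim depend on the per-protocol (PP) result, and the protocol's rule for skipping PP checks who is in the sets but not which drug each child received

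*Protocol*

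**What the plan says.** Protocol 9.3 groups the two efficacy sets differently. For the primary set, "The ITT population will include subjects as randomized"; for the secondary set, "The PP population will include subjects as treated". The same section sets a skip rule, which opens "If the PP and ITT populations are exactly the same and there are no missing data" and goes on to cancel the PP efficacy analysis.

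Protocol 9.4.6 describes the role of PP without that exception: "Analyses will be performed primarily on the ITT population and will be repeated on the PP population to determine robustness of results". The SAP also has no exception. Section 2.9.1 says "The primary efficacy endpoint will also be analyzed for the PP population", and section 4.5.1 assigns the result to Table 2.1.2.

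SAP 3.1 provides for a wrong-drug child within PP: "In case there is a difference between treatment assigned and received, treatment actually received will be utilized" to define the arm. Such a child can therefore remain in PP and change arms.

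The documents differ on who decides PP membership. Protocol 9.3 uses a masked evaluation before unmasking; SAP 3.1 leaves the judgement to the investigator.

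The claim is one of no difference. Protocol 9.1 and 9.4.6 accept the null hypothesis when P exceeds 0.05, with no margin. SAP 2.9.1 adds a 90% CI within ±20% of the reference. Neither says what follows if ITT meets the criterion and PP does not.

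**The concern.** When the aim is to show that two drugs do not differ, an as-randomised analysis is not automatically the cautious one. A child who receives the other arm's drug makes the arms look more alike, which helps the claim. The usual protection is to ask that the PP analysis agree. Here PP is planned, but nothing depends on its result.

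The skip rule adds a second, narrower gap. Omitting PP is harmless only if the same children must give the same result. Under the plan's own definitions they need not, because a child can sit in one arm in ITT and in the other in PP. The rule tests membership and missing data but not received drug. It could therefore remove the as-treated efficacy analysis when relabelling is the only difference between the sets. Protocol and SAP also disagree on whether PP is run in that case.

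**Working it through.** **Inputs from the documents.** At least 60 evaluable children at 1:1, so 30 per arm (Protocol 9.2). Pearson chi-square test, with no difference claimed if P > 0.05 (Protocol 9.4.6). A 90% CI from an ANOVA, within ±20% of the reference (SAP 2.9.1). The sample size was directed by the regulator and comes with no power, response rate or dropout rate, so there is no planned figure to reproduce on this point.

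**Assumptions.** All response rates, response counts and mis-dosing counts are assumed, since the documents give none. The ±20 is read as absolute percentage points. The ANOVA interval is computed without the eye-side factor, as a pooled-variance t interval on 58 degrees of freedom.

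**Step 1: can identical children give different results?** Take 27/30 successes on AG-920 and 29/30 on Proparacaine as randomised. Suppose one kit swap: an AG-920-assigned success received Proparacaine, and the Proparacaine-assigned failure received AG-920. As treated, the counts are 26/30 and 30/30. The same 60 children are in both sets and nothing is missing, so on a membership reading the skip rule applies if both children stay in PP.

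Let p1 and p2 be the observed proportions and d = p1 − p2.
- 90% CI: d ± 1.672 × √(s² × 2/30), with s² = 30 × [p1(1 − p1) + p2(1 − p2)] / 58.
- Chi-square: d² / [p(1 − p) × 2/30], with p = 56/60 in both tables, so the denominator is 0.004148.

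| | ITT, as randomised | PP, as treated |
|---|---|---|
| d | −0.067 | −0.133 |
| s² | 3.667/58 = 0.0632 | 3.467/58 = 0.0598 |
| Half-width | 1.672 × 0.0649 = 0.109 | 1.672 × 0.0631 = 0.106 |
| 90% CI | −0.175 to 0.042 (met) | −0.239 to −0.028 (not met) |
| Chi-square | 0.004444/0.004148 = 1.07 | 0.017778/0.004148 = 4.29 |
| P | 0.30 (no difference) | 0.038 (difference) |

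Both criteria reverse in this example. They need not. If all 60 children succeed, one wrong-drug child turns 30/30 v 30/30 into 29/29 v 31/31, and the difference is zero both ways. Swapping two children with the same outcome changes nothing. With 27/30 v 30/30, one AG-920-assigned success given Proparacaine gives 26/29 v 31/31: P moves from 0.0756 to 0.0662 and the conclusion stands.

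**Step 2: how far does mis-dosing help the claim on ITT?** Let k children per arm receive the other drug. The expected ITT difference is the true difference × (1 − 2k/30). With true rates of 75% and 95%:
- k = 0: 20.0 points
- k = 1: 20 × 28/30 = 18.7 points
- k = 2: 20 × 26/30 = 17.3 points

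Successes in each arm are the sum of a binomial on 30 − k children at that arm's own rate and a binomial on k children at the other rate. Enumerating all pairs of counts exactly gives the chance of claiming no difference or equivalence:

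| k per arm | 90% CI within ±20 points (SAP) | P > 0.05 (Protocol) |
|---|---|---|
| 0 | 7.0% | 36.7% |
| 1 | 8.7% | 43.6% |
| 2 | 10.7% | 50.5% |

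Only the increase over k = 0 belongs to this point: 1.7 and 3.7 percentage points under the SAP criterion. The 7.0% and 36.7% starting values come from the criteria themselves.

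**The case against.** A reader might infer three stronger things, and the documents do not support them.
- *That the claim is tested on ITT only.* PP is a planned robustness repeat in Protocol 9.4.6 and is planned without condition in SAP 2.9.1 and 4.5.1. What is missing is a rule that the claim depends on it.
- *That PP is the only as-treated analysis.* This is true for efficacy only; the safety population is also summarised as treated.
- *That any wrong-drug child would change the result.* The result could change but need not, as Step 1 shows.

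The skip also bites only when several things coincide. A child must receive the wrong drug, that child must be kept in PP, no one else may be excluded, and no data may be missing. If a wrong drug is ruled a major violation, the child leaves PP, the sets differ and PP is run. Neither document says whether it is one. Other major deviations likewise take a child out of PP, so the skip cannot hide them. Populations with different arm labels might also be read as not the same, though Protocol 9.3 calls PP a subset of ITT, which points to membership.

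Mis-dosing looks unlikely. There is one dose, the containers differ, staff are not masked, and they retrieve the assigned kit number before dosing. SAP Listing 3 would show assigned and received drug for every randomised child. All of this stands and keeps the point small. A listing makes a mix-up visible, however, and does not replace the analysis.

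A last objection is that making PP decisive hands influence to whoever judges membership, who under SAP 3.1 is the unmasked investigator. That is a reason to settle membership by masked evaluation. It does not defeat the joint requirement, because requiring both sets can only lower the false-claim rate relative to ITT alone.

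**Conclusion.** The point holds in a limited form. No rule ties the no-difference or equivalence claim to PP, and the Protocol 9.3 skip condition is unsound under the plan's own definitions because it ignores received drug. The SAP has no matching clause, so the documents also disagree.

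The skip has no effect if no child is mis-dosed, which may well be the case. The increases of 1.7 and 3.7 points assume symmetric mis-dosing in both arms, true rates exactly 20 points apart, 30 per arm and an absolute margin. If the SAP's ±20% is relative to the reference, the limit at a 95% rate would be 0.20 × 95 = 19 points and the figures would change. This is a cheap improvement to the wording; it is not a flaw that threatens the trial.

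**What to change.** 1. In Protocol 9.3, delete the skip sentence so that it matches the SAP. Alternatively, add the condition *and no subject received a treatment other than the one assigned*, and put the same sentence in the SAP.
2. In Protocol 9.4.6 and SAP 2.9.1, state that equivalence or non-inferiority is claimed only if the criterion is met in both ITT and PP.
3. In SAP 3.1, replace the investigator's judgement of PP membership with the masked evaluation in Protocol 9.3.

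The cost is a few sentences. The SAP already plans the PP table, so no new analysis is needed. The downside is a slightly lower chance of making the claim if the two sets disagree.
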